6.1 Analysis of Primary Endpoints

All primary and secondary endpoints efficacy and safety endpoints will be evaluated in the intent to treat and per protocol samples. Additionally, the primary safety and specified adverse events will be evaluated in the as treated sample.

6.1.1 Definition of Analysis Samples

1. Target Population

The target population for the INVEST registry are adult patients who have a diagnosis of supratentorial intracranial hemorrhage who do not require emergent open surgical decompression related to uncontrolled intracranial pressure or mass effect, who do not qualify for the INVEST multi-center Feasibility study and who are to be treated with Apollo / Artemis MIES at an INVEST center.

2. Intent to Treat Sample

As the primary analysis, all efficacy and safety outcome measures will be analyzed under the intent-to-treat (ITT) principle. Under this principle, the evaluable sample includes all subjects who are enrolled.

3. Per Protocol Sample

In addition to the defined ITT analysis sample, a per-protocol sample is defined as a subset of the ITT sample. This sample will be used for secondary sensitivity analyses of the primary and secondary outcomes.

The per-protocol sample will include all subjects that do not have the following protocol violations or deviations:

- a. Eligibility violation
- b. Treatment failure (no Apollo / Artemis MIES performed)
- c. Missing 180-day primary efficacy outcome (not including missing due to death prior to the 180 days)
- 4. As Treated Sample

This sample will be used for analyses of the safety outcomes. The as treated sample will include all subjects that are enrolled and have Apollo / Artemis MIES performed.

7. General Statistical Considerations

General Design Issues

The primary objective of this multicenter prospective registry is to provide additional safety, technical outcomes and

clinical outcomes data for minimally invasive endoscopic surgery (MIES) with Apollo / Artemis for the evacuation of brain hemorrhage in patients who do not qualify for the concurrent INVEST feasibility study at active INVEST centers. This structure will allow INVEST centers to consider all patients presenting with intracranial hemorrhage who are potentially candidates for the Apollo / Artemis MIES procedure for a clinical research trial, which will facilitate enrollment as well as protocol familiarity and adherence. This structure will also yield the highest possible amount of data about this new procedure.

General Statistical Methods

As a single arm registry, all statistics reported for the entire cohort as well as subgroups will be purely descriptive. All confidence intervals presented will be two-sided. Statistical tests between subgroups will be two-tailed with a significance level of 0.05. Summary tables (descriptive statistics and/or frequency tables) will be provided for all baseline variables, effectiveness variables, and safety variables, as appropriate. Continuous variables will be summarized with descriptive statistics (n, mean, standard deviation, range, and median). Frequency counts and percentage of subjects within each category will be provided for categorical data. The specific details of the statistical analyses will be described completely in the statistical analysis plan. The statistical analysis plan will be finalized prior to database lock.

Results collected at multiple visits will be summarized at each visit for which they are collected as described in **Table 1 Schedule of Events**. Summaries for all measures will include all observed data for each visit.

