7.2 Statistical Evaluation of Primary Endpoint

Statistical Analysis of Primary Clinical Efficacy Outcome

The primary clinical efficacy endpoint will be calculated as the proportion of subjects with a 180 day mRS of 0 to 3. Subjects who die prior to the 180 day mRS assessment will be included in the analysis with an mRS score of 6. The proportion of patients with favorable clinical outcomes based on this criterian will be calculated, and a 95% confidence interval will be presented. The number and percentage of subjects in each mRS category (0 to 6) will also be presented.

Statistical Analysis of Primary Technical Efficacy Outcome

The proportion of subjects experiencing surgical success based on the following criteria will be calculated, and a 95% confidence interval will be presented.

- Predominantly or Only ICH: Reduction to < 15 cc total volume AND >60% reduction in hemorrhage volume on immediate post-treatment CT scan
- $\circ~$ Predominantly or Only IVH: mGraeb score of < 5 on day 7 CT scan

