7.3 Missing Data and Imputation Methods

Under the ITT principle, all patients who are enrolled are included in the analysis. Therefore, missing data, especially in the outcome measures, can be problematic. Every effort is to be made to keep all missing data, particularly the Day 180 outcomes, to a minimum. Despite the clinical sites' best efforts, some missing data may be inevitable mainly due to lost-to-follow-up (LTFU). The number and proportion of subjects eligible for and compliant with each follow-up examination will be presented. Subjects who withdraw from the study will be tabulated with reasons for withdrawal. Since the primary endpoint is defined using mRS, subjects deceased during study follow-up will be scored as mRS 6. Other subjects not completing the 180-day follow-up visit will be categorized for the primary endpoint using the mRS as of the last available follow-up visit or discharge (whichever is later). As a sensitivity analysis, we will also perform analysis after excluding subjects without 180-day follow-up evaluations. Additional details will be provided in the Statistical Analysis Plan (SAP).

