7.4 Secondary Statistical Analysis

7.4.1 Secondary Endpoints

The secondary effectiveness variables:

- mRS at 30 and 90 days The number and percentage of subjects who experience mRS 0 to 3 will be calculated along with the 95% confidence interval. Frequency counts and percentage of subjects within each category will be provided.
- Length of hospital stay The median total length of stay and median ICU length of stay along with the interquartile range will be provided.
- Requirement for VPS The number and percentage of subjects who have VPS placement will be calculated along with the 95% confidence interval.

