7.5 Safety Analysis

7.5.1 Safety Outcomes

Several specific adverse events are monitored throughout the study. However the primary safety outcome to be assessed at completion of the trial will be death within 30 days.

The proportion of deaths for any reason through 30 days will be calculated and a 95% confidence interval will be presented. Survival estimates will be generated to evaluate the time-to-death using the Kaplan-Meier methodology for all deaths through 30 days.

All adverse events will be summarized by showing the number and percent of patients which report the event. Events will also be reported by relationship to the procedure or device.

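### Per-protocol criterion (c), a missing 180-day mRS, also removes subjects from 30-day mortality, surgical success and other endpoints already observed well before day 180

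*Combined protocol and SAP*

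**What the plan says.** Section 6.1 sets the scope: "All primary and secondary endpoints efficacy and safety endpoints will be evaluated in the intent to treat and per protocol samples". Section 6.1.1 makes ITT (all enrolled subjects) the primary analysis. It then defines one per-protocol subset by three exclusions: (a) an eligibility violation, (b) no Apollo/Artemis procedure performed, and (c) "Missing 180-day primary efficacy outcome (not including missing due to death prior to the 180 days". Of this subset it says: "This sample will be used for secondary sensitivity analyses of the primary and secondary outcomes". No version of (c) specific to an endpoint appears. The primary safety endpoint and the specified adverse events are also analysed as treated, in enrolled subjects who had the procedure, with no condition on day 180.

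Several endpoints in this scope are settled long before day 180:

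- **Safety (7.5.1):** "The proportion of deaths for any reason through 30 days will be calculated and a 95% confidence interval will be presented".
- **Technical success (7.2):** "The proportion of subjects experiencing surgical success based on the following criteria will be calculated, and a 95% confidence interval will be presented". The criteria are read on the CT directly after treatment for ICH and on the day 7 CT for IVH.
- **Secondary endpoints (7.4.1):** 30- and 90-day mRS, shunt placement, and length of stay, for which "The median total length of stay and median ICU length of stay along with the interquartile range will be provided".

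On missing data, section 7.3 first says of deaths: "Since the primary endpoint is defined using mRS, subjects deceased during study follow-up will be scored as mRS 6". It then carries the last available mRS forward for the other subjects without a 180-day visit, and adds: "As a sensitivity analysis, we will also perform analysis after excluding subjects without 180-day follow-up evaluations". Unlike 6.1.1(c), that last sentence states no exception for death.

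**The concern.** A subject followed to day 100 and then lost has complete information on 30-day death, on the post-treatment or day 7 CT, on hospital stay, and on the 30- and 90-day mRS. Under (c) that subject leaves the per-protocol analysis of all of these because a later, different measurement is missing.

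For mortality the removal is one-sided. A subject who died cannot be removed by (c), and a survivor lost later can. The numerator is protected and the denominator shrinks, so per-protocol mortality moves away from ITT mortality for a reason unrelated to day 30.

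The registry is descriptive (section 7), so its percentages are its results. A per-protocol analysis should show what eligibility violations and untreated subjects contribute. The as-treated sample already handles (b), so per-protocol mortality differs from as-treated mortality only through (a) and (c). Criterion (c) thus mixes late loss to follow-up into the one comparison that the per-protocol sample adds for safety.

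**Working it through.** **Inputs.**
- Attrition of 10%, 200 enrolled and 180 at day 180: section 7.1.
- Enrolment of up to 50: synopsis and section 4.5. The disagreement between 50 and 200 is a separate matter; the factor below depends only on the share removed.
- 30-day mortality (10% to 40%) and surgical success (70%): assumptions, because the documents give neither. The numbers removed are also assumptions, up to the plan's 10%.

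**The plan's own figures.** 200 × (1 − 0.10) = 180, as stated. For 61/180 = 33.9%, the normal-approximation half-width is 1.96 × √(0.339 × 0.661/180) = 6.9 points, giving 27.0% to 40.8%, which matches the stated 27% to 41%. Neither figure is disputed.

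**Step 1: effect of (c) on 30-day mortality.** Let N be enrolled, D deaths by day 30, and L subjects not known to have died who lack a 180-day mRS. Suppose nobody falls under (a) or (b), so that (c) acts alone.
- ITT rate = D/N.
- Per-protocol rate = D/(N − L).
- Ratio = N/(N − L) = 1/(1 − L/N), which is never below 1.

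Deaths between day 30 and day 180 stay in the denominator under both rules.

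**Step 2: size.** With N = 50 and an assumed D = 10, exact (Clopper-Pearson) 95% intervals:

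| Removed by (c) | Rate | 95% CI | Factor |
|---|---|---|---|
| 0 | 10/50 = 20.0% | 10.0% to 33.7% | 1.000 |
| 1 | 10/49 = 20.4% | 10.2% to 34.3% | 1.020 |
| 3 | 10/47 = 21.3% | 10.7% to 35.7% | 1.064 |
| 5 | 10/45 = 22.2% | 11.2% to 37.1% | 1.111 |

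At other assumed rates with 5 removed: 5/50 = 10.0% becomes 5/45 = 11.1%; 15/50 = 30.0% becomes 15/45 = 33.3%; 20/50 = 40.0% becomes 20/45 = 44.4%. With N = 200 and 20 removed, 40/200 = 20.0% becomes 40/180 = 22.2%, the same factor.

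The factor 1/0.9 = 1.11 is a ceiling at the plan's attrition. It needs all 10% to be subjects alive at day 30 and not known to have died later. Section 7.1 does not say whether its attrition includes deaths; if it does, L is smaller and so is the factor.

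**Step 3: surgical success.** Take an assumed 35/50 = 70.0% and remove 5 subjects.
- If they resemble the rest (4 or 3 successes among the 5): 31/45 = 68.9% or 32/45 = 71.1%.
- Extremes: all 5 successes, 30/45 = 66.7%; all 5 failures, 35/45 = 77.8%.

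The direction cannot be known in advance. The same holds for length of stay, shunt placement and 30- and 90-day mRS.

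**The case against.** The strongest reply concerns weight. ITT is primary for every outcome. Thirty-day mortality is also reported as treated, and 7.5.1 adds a Kaplan-Meier estimate through day 30. Section 7 undertakes to summarise all data observed at each visit, so the 30- and 90-day mRS will appear in full at least in the ITT sample. One common per-protocol set for all endpoints is a familiar convention. The mortality shift, 0.4 to 2.2 points at an assumed 20%, is small beside an interval of 10.0% to 33.7%. Some subjects removed by (c) may have been lost before day 30, and dropping those is not clearly a distortion, since a raw proportion that keeps them counts them as alive. All of this stands, and it makes the point minor. It does not justify removing subjects whose day-30 status or CT result is known. Nor does the SAP deferral settle it: section 6.1.1 already fixes (c), although the SAP is a convenient place for the clarification.

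A reader might infer something stronger from 7.3: that its sensitivity analysis drops the deaths and so raises the mRS 0–3 rate. The documents do not support that as the plan's intent. Sections 7.2 and 7.3 both score deaths as mRS 6, the sentence just before the sensitivity sentence deals with the subjects who did not die, and 6.1.1(c) states the exception outright. What remains is an omission that permits a literal misreading. No magnitude is attached to it here, because any figure would rest on the less likely reading and on an assumed number of deaths.

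**Conclusion.** The point holds and is minor. As written, (c) governs every per-protocol endpoint. Acting alone, it can raise per-protocol 30-day mortality or leave it unchanged, never lower it. The increase is at most about 1.11-fold at the plan's 10% attrition, or 1.1 to 4.4 points for assumed mortality of 10% to 40%. It is less if that attrition includes deaths or falls partly on subjects lost before day 30 whom any analysis of observed data would also omit. For the other early endpoints the cost is discarded valid data, with a shift of unknown direction. The sign of the mortality effect follows from the definition; its size rests on the assumed death and removal counts.

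A reader should not conclude that the registry's primary safety or technical results are biased by this. The ITT analyses and as-treated mortality do not use (c).

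**What to change.** In 6.1.1, add after the list of exclusions:

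> Criterion (c) applies only to the analysis of the 180-day mRS; other endpoints use all subjects free of violations (a) and (b) with that endpoint observed.

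For 30-day mortality, observed means that vital status at day 30 is known. For the 30- and 90-day mRS, a death before the visit should count as observed, in line with the mRS 6 scoring, so that this sentence does not itself remove deaths.

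As a minor clarification, add to 7.3:

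> For the 180-day mRS, deaths before day 180 remain as mRS 6; the sensitivity analysis excludes only subjects not known to have died who lack a 180-day mRS.

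The limit to the 180-day mRS matters: a broader rule scoring deaths as 6 in every analysis could overwrite 30- and 90-day values recorded before a later death. With this clause, the 7.3 analysis is a clean check of carry-forward in the ITT sample.

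The cost is one sentence in each section, or both in the SAP, which is to be finalised before database lock. No new data are needed and no primary analysis changes.

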INVEST-REGISTRY: Minimally Invasive Endoscopic Surgical Treatment With Apollo/Artemis in Patients With Brain Hemorrhage: A Prospective Multicenter Registry [name] NCT02661672 Document Date: 10-24-2017

INVEST-REGISTRY: Minimally Invasive Endoscopic Surgical Treatment with Apollo / Artemis in patients with Brain Hemorrhage: A Prospective Multicenter Registry

[name] Mount Sinai School of Medicine

[name] Stony Brook Medical Center

[name] Semmes-Murphy Clinic

Version 1.0	11-5-2015
Version 2.0	03-30-2017
Version 3.0	10-24-2017

Study Title: INVEST REGISTRY: Minimally Invasive Endoscopic Surgical Treatment with Apollo / Artemis in patients with Brain Hemorrhage: A Prospective Multicenter Registry

Version Number: 3

Version Date: 10-24-2017

Study Center:

I, the undersigned, have read and understand the protocol specified above and agree on its content. I agree to perform and conduct the study as described in the protocol and in accordance with the relevant parts of the appropriate regulatory requirements and the pertinent individual country laws/regulations.

Investigator	
Print name:	

Date

Primary Contacts

Penumbra Inc.
[name]
Statistical and Data Management Center
Mount Sinai School of Medicine
[name]
Statistical and Data Management Center Mount Sinai School of Medicine [name]
[name]
Oculus Imaging LLC
[name]
[name]
-

Study Synopsis:

Title: INVEST REGISTRY: Minimally Invasive Endoscopic Surgical Treatment with Apollo / Artemis in patients with Brain Hemorrhage: A Prospective Multicenter Registry

Objective: The primary objective of this multicenter prospective registry is to provide additional safety, technical outcomes and clinical outcomes data for minimally invasive endoscopic surgery (MIES) with Apollo / Artemis for the evacuation of supratentorial brain hemorrhage in adult patients who do not qualify for the concurrent INVEST Feasibility study at active United States (US) INVEST centers.

Study Design: This study will be a prospective, non-randomized, multi-center, single arm registry that will enroll up to 50 patients at up to 30 US centers.

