As discussed in detail in the companion INVEST submission, intracranial hemorrhage is a devastating disease associated with poor clinical outcomes. To date, no surgical or medical therapy (with the exception of blood pressure management) has been demonstrated to definitively improve outcomes in these patients. Of all the interventional therapeutic strategies tested, the most encouraging data exist for minimally invasive surgery¹. The primary aim of minimally invasive surgery (MIS) for brain hemorrhage is to achieve an atraumatic evacuation of blood products from the brain to prevent the secondary injury that occurs after the initial bleed. To date, several pilot studies and a small Phase II feasibility trial have suggested that MIS with catheter mediated thrombolytic irrigation may be associated with an improvement in clinical outcomes in ICH. Similarly, pilot studies have indicated that catheter mediated lysis and drainage of hemorrhage from the ventricular system may be clinically beneficial². While, initial data derived from these preliminary studies of thrombolytic-assisted catheter drainage have been encouraging, but there are significant potential shortcomings of this technique compared to the purely mechanical approach with the Apollo system or Artemis Device.

2. Purpose and Hypothesis

The Artemis Device or its predecessor the Apollo System have been commercially available in the US for the surgery in the ventricular system or cerebrum for over three years and early experience with the system in regards to its application to remove parenchymal and intraventricular hemorrhages has evolved^{1, 3, 4}. As such, now that the technical approach has matured, it is necessary to proceed with a feasibility study to assess the potential clinical impact of the Artemis system in patients with supratentorial ICH. Currently no prospective study of any kind has evaluated the efficacy minimally invasive endoscopic surgery (MIES) with the Apollo or Artemis system for brain hemorrhages. The purpose of this prospective registry is to capture data from patients who do not qualify for INVEST feasibility study, but who undergo Apollo or Artemis treatment at participating US INVEST centers. We anticipate that these registry data will be useful to more fully understand the Apollo and/or Artemis procedure. Since this is a single-arm study of Apollo / Artemis MIES treatment, a formal hypothesis test is not planned.

Rationale for the INVEST Registry Design

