4.4 Study Visits

Subjects enrolled to this study will follow the below visits schedule according to standard of care for stroke patient follow-up.

- Pre-Treatment
- Procedure
- Post procedure (24 hours, Apollo / Artemis MIES patients)
- 7 days post-enrollment or Discharge (whichever comes first)
- 1 month follow-up (+/- 14 days)
- 3 month follow-up (+/- 21 days)
- 6 month follow-up (+/- 28 days)

4.5 *Recruitment*

The target population for the INVEST registry are adult patients who have a diagnosis of supratentorial intracranial hemorrhage who do not require emergent open surgical decompression related to uncontrolled intracranial pressure or mass effect, who do not qualify for the INVEST multi-center Feasibility and who are to be treated with Apollo or Artemis MIES at an INVEST center.

Potential study participants and/or their legal authorized representative will be identified by the study team at each site to obtain consent and determine eligibility. Up to 30 United States sites will be included in this study and enroll up to 50 patients.

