7.1 Sample Size Justification

Sample Size Calculation

The proposed study is a single-arm registry which will run concurrently with the INVEST feasibility study. A sample size of 200 provides 180 subjects at 180 days, with an estimated 10% attrition rate. Since this is a single- arm study of Apollo / Artemis MIES treatment, a formal hypothesis test is not planned. Assuming an effectiveness primary endpoint response rate for mRS 0 to 3 of 34% (61/180), the expected normal approximation to the binomial two-sided 95% confidence interval around the primary endpoint rate is (27%, 41%). Hence, the proposed sample size provides a precision estimate of \pm 7% which is sufficient to assess the Apollo / Artemis MIES treatment. The precision for the estimated single proportion was calculated using SAS v 9.4 (SAS Institute, Cary, NC).

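### Section 7 calls all subgroup statistics purely descriptive, yet sets a 0.05 significance level for subgroup tests that it neither names, limits nor labels exploratory

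*Combined protocol and SAP*

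**What the plan says.** The paragraph under General Statistical Methods in section 7 opens by saying that "all statistics reported for the entire cohort as well as subgroups will be purely descriptive". One sentence on the two-sidedness of confidence intervals follows, and then: "Statistical tests between subgroups will be two-tailed with a significance level of 0.05". The same paragraph leaves the details to a SAP that is to be final before database lock. No separate SAP text is in the supplied document.

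Sections 2 and 7.1 both state that "a formal hypothesis test is not planned", and both give the single-arm design as the reason.

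The analysis sections (7.2, 7.4.1 and 7.5.1) specify proportions with 95% confidence intervals, category counts, medians with interquartile ranges and Kaplan-Meier estimates. None of them specifies a test or a subgroup.

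On size, the synopsis says the registry will "enroll up to 50 patients at up to 30 US centers", and section 4.5 repeats the cap of 50. Section 7.1 instead says: "A sample size of 200 provides 180 subjects at 180 days, with an estimated 10% attrition rate".

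**The concern.** A significance level has a use only if a result is to be declared on one side of it or the other, and that is not description. The opening sentence covers subgroups explicitly, so the conflict cannot be resolved by taking it to mean whole-cohort statistics only.

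The supplied text does not limit what may be tested. The registry is unblinded (section 7.6) and the SAP need only be final by database lock, so subgroups could be chosen after outcomes are known.

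At stake is how the final report words its subgroup findings. The design rationale in section 2 says the data may inform a later pivotal trial. A difference called significant could carry more weight there than it has earned. In a small registry, a difference called non-significant could be taken as evidence that subgroups respond alike.

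**Working it through.** **1. The text side by side.** Sentence one of the paragraph: subgroup statistics are descriptive only. Sentence two: confidence intervals are two-sided. Sentence three: subgroup tests use a two-tailed 0.05 level. Sentences one and three conflict; sentence two is compatible with both.

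**2. The plan's own figure.** Section 7.1 gives 34% (61/180) with a 95% interval of 27% to 41%. The normal approximation is p ± 1.96·√(p(1−p)/n). With p = 61/180 = 0.339 and n = 180, the half-width is 0.069 and the interval is 27.0% to 40.8%. With 10% attrition, 180/0.90 = 200. Both figures reproduce. At n = 50 and p = 0.34 the same formula gives ±13.1 points (20.9% to 47.1%). The plan gives no figure for any subgroup comparison at either size.

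**3. False positives (illustration).** There are three primary endpoints (180-day mRS, surgical success, 30-day mortality) and four secondary ones (mRS at 30 days, mRS at 90 days, length of stay, VPS). Testing one two-level subgroup factor on each is an assumption; it gives seven tests.

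- Independent tests at full nominal size: 1 − 0.95^7 = 0.302, about 30%.
- A Fisher exact test (also an assumption, since no test is named) with a true rate of 34% in both groups has actual size 2.5% at 25 v 25 and 3.2% at 40 v 10. Seven independent tests of that size would give 1 − 0.975^7 ≈ 16% and 1 − 0.968^7 ≈ 20%. Length of stay is not binary, so this only shows the direction.
- Deaths count as mRS 6, so mRS at the three time points and 30-day mortality overlap. Positive correlation of this kind lowers the chance further.

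**4. Power at the cap of 50.** Assume 44% v 24% favourable mRS, a 20-point difference centred on 34%. For n per group, the normal-approximation power is Φ[(d − 1.96·√(2p̄(1−p̄)/n)) / √((p1(1−p1)+p2(1−p2))/n)].

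- 25 v 25: √(2·0.34·0.66/25) = 0.134, and 1.96 × 0.134 = 0.263. The denominator is √((0.2464+0.1824)/25) = 0.131. So Φ[(0.20 − 0.263)/0.131] = Φ(−0.48) ≈ 32%. Exact enumeration with Fisher's test gives 23%.
- 40 v 10: 19% by the approximation and 15% by Fisher.
- Smallest difference with 80% power by the approximation: about 37 points (52.5% v 15.5%) at 25 v 25, and about 19 points (43.5% v 24.5%) at 100 v 100. Detecting 44% v 24% with 80% power needs about 87 per subgroup.

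**5. What an interval would show instead.** For the same 25 v 25 case, if 44% and 24% were observed, the difference would be 20 ± 1.96 × 13.1 = 20 ± 25.7 points, that is −6 to 46. The uncertainty is visible without a threshold.

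**The case against.** The strongest reply is that the sentence only fixes sidedness and level for any comparison that happens to be made. It commits the sponsor to no test, claim or success rule; the analysis sections contain no test; and the SAP may supply the limits. Much of that stands, and it rules out several stronger readings that a reader might infer.

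- **That sections 2 and 7.1 forbid all testing.** They exclude a formal test because there is no control arm. That concerns the treatment effect, and informal contrasts within the arm do not contradict it. The conflict lies within the section 7 paragraph.
- **That the plan as a whole has no multiplicity control.** This can be said only of the supplied text, because details are deferred to the SAP.
- **That subgroup p-values would be uninterpretable.** Nominal p-values clearly labelled exploratory can be read in a registry with no confirmatory hypothesis. The fault is that no such label is required.
- **That false positives are bound to be very frequent.** Ten or twenty independent tests would give 40% or 64%, but no such count is in the documents, and independence is unrealistic here.
- **That these tests would settle who enters a Phase III trial.** The rationale says only that the data may be informative. Its worked example, low GCS, compares registry patients with feasibility-study patients, not two registry subgroups.
- **That the sample is settled at 50.** Section 7.1 is built on 200.

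The reply does not remove the conflict itself: a descriptive-only statement about subgroups and a significance level for subgroup tests stand in one paragraph, with nothing to say which governs.

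**Conclusion.** The point holds as an internal inconsistency of minor severity. Followed as written, the plan allows subgroup differences to be called significant at 0.05 with no false-positive control in the supplied text.

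The chance of at least one false positive is about 30% for one factor across seven endpoints. That figure assumes one factor, seven tests, independence and full nominal size; relaxing either of the last two brings it down. Low power matters as much: about 23% to 32% for a 20-point difference in an assumed 25 v 25 split of 50 patients, so a non-significant result would mislead too. If 200 is the true target, power improves, but even 100 v 100 needs about 19 points for 80% power.

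No primary conclusion depends on these tests.

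**What to change.** Delete the significance-level sentence from section 7. Report subgroup estimates and differences with two-sided 95% confidence intervals, labelled exploratory and unadjusted for multiplicity. This fits the descriptive purpose that the paragraph already states.

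If the sponsor wants to keep p-values, name the subgroups and endpoints in the SAP and label the p-values nominal and exploratory, with no significance threshold.

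Separately, reconcile the cap of 50 (synopsis and section 4.5) with the 200 in section 7.1, so that the precision of any subgroup estimate can be stated.

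The cost is one sentence of text and the loss of subgroup significance statements. No new data are needed, and the primary analyses do not change.
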